13.4.4 Analyses of Secondary and Other Endpoint(s)/Outcome(s)

Secondary Endpoints, Lesional AD skin:

1. The abundance of the AMT bacterial strains on lesional skin at baseline and after 1 week BID application of AMT.
 - a. The abundance of live *CoNS* species on lesional skin will be compared from baseline (day 28) to Day 35 after 1 week BID application of AMT cream versus placebo. This will be calculated using a two-tailed t-test for independent samples with type II error rate of 0.2 and type I error rate of 0.05.
2. The quantity of transplanted bacteria on lesional skin after stopping AMT cream 1 day, 2 days, and 4 days after last application.
 - a. Live antimicrobial *Staph* species will be measured on lesional skin at baseline (day 28), Day 35 (after 7 days of cream application), Day 36, Day 37, and Day 39 in order to evaluate the abundance of the antimicrobial *CoNS* species that remains after

stopping cream application. In order to take into account the variance of the abundance of antimicrobial *CoNS* species found on each subject's skin at baseline, we will perform CFU counts at each time point (Day 28, 35, 36, 37, and 38) and evaluate the percentage of antimicrobial species present at each time point. The percentage of antimicrobial species present at each time point will be compared between the AMT cream arm and placebo arm using a two-tailed t-test for independent samples with type II error rate of 0.2 and type I error rate of 0.05.

3. The change in abundance of *Staph aureus* on lesional skin from baseline to 1 day, 2 days, and 4 days after stopping AMT.
 - a. The abundance of live *Staph aureus* on lesional skin will be evaluated using CFU counting at baseline, 1 hour, and 4 hours after initial application of AMT or placebo cream, and after 4 and 7 days of cream application. At each time point, we will compare the AMT cream and placebo arms by using a two-tailed t-test for independent samples with a type I error rate of 0.05 and type II error rate of 0.2.
4. Change in clinical assessments, including SCORAD, modified EASI, and EASI after 1 week BID application of AMT.
 - a. A modified EASI, global SCORAD and EASI score will be assessed at baseline 1 week BID application of AMT cream or vehicle cream. Using percentage of improvement of these scores, we will compare percent reduction of AD severity between AMT cream and placebo cream using a two-tailed t-test with type I error rate of 0.05.
5. Identify lesional skin microbiome by DNA sequencing from baseline and after 1 week BID application of AMT.
 - a. Using DNA sequencing, the microbiome of lesional skin will be identified at baseline and after 1 week BID application of AMT.
6. Evaluate the lesional skin microbiome transcriptome by RNA-sequencing analysis from baseline and after 1 week BID application of AMT.
 - a. Using RNA-sequencing analysis, the microbiome of lesional skin will be evaluated at baseline and after 1 week BID application of AMT.

Secondary Endpoints, Non-lesional skin:

1. The abundance of *Staph aureus* at baseline and after 1 week BID application of AMT on non-lesional skin.
 - a. The abundance of *Staph aureus* on non-lesional skin will be compared from baseline (day 28) to Day 35 after 1 week BID application of AMT cream versus placebo. This will be calculated using a two-tailed t-test for independent samples with type II error rate of 0.2 and type I error rate of 0.05.
2. The abundance of the AMT bacterial strains on non-lesional skin after 1 week BID application of AMT.
 - a. The abundance of live *CoNS* species on non-lesional skin will be compared from baseline (day 28) to Day 35 after 1 week BID application of AMT cream versus placebo. This will be calculated using a two-tailed t-test for independent samples with type II error rate of 0.2 and type I error rate of 0.05.
3. The quantity of transplanted bacteria on non-lesional skin after stopping AMT cream 1 day, 2 days, and 4 days after last application.

- a. Live antimicrobial *Staph* species will be measured on non-lesional skin at baseline (day 28), Day 35 (after 7 days of cream application), Day 36, Day 37, and Day 39 in order to evaluate the abundance of the antimicrobial *CoNS* species that remains after stopping cream application. In order to take into account the variance of the abundance of antimicrobial *CoNS* species found on each subject's skin at baseline, we will perform CFU counts at each time point (Day 28, 35, 36, 37, and 38) and evaluate the percentage of antimicrobial species present at each time point. The percentage of antimicrobial species present at each time point will be compared between the AMT cream arm and placebo arm using a two-tailed t-test for independent samples with type II error rate of 0.2 and type I error rate of 0.05.
4. The change in abundance of *Staph aureus* on non-lesional skin from baseline to 1 day, 2 days, and 4 days after stopping AMT.
 - a. The abundance of live *Staph aureus* on non-lesional skin will be evaluated using CFU counting at baseline, 1 hour, and 4 hours after initial application of AMT or placebo cream, and after 4 and 7 days of cream application. At each time point, we will compare the AMT cream and placebo arms by using a two-tailed t-test for independent samples with a type I error rate of 0.05 and type II error rate of 0.2.
5. Identify lesional skin microbiome by DNA sequencing from baseline and after 1 week BID application of AMT.
 - a. Using DNA sequencing, the microbiome of lesional skin will be identified at baseline and after 1 week BID application of AMT.
6. Evaluate the lesional skin microbiome transcriptome by RNA-sequencing analysis from baseline and after 1 week BID application of AMT.
 - a. Using RNA-sequencing analysis, the microbiome of lesional skin will be evaluated at baseline and after 1 week BID application of AMT.

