1.1. Background and Scientific Rationale

It is essential for microbial communities to reside on our epithelial surfaces to maintain several functions of human health (1-3). This conclusion is based in part on observations that dysbiosis, a state of microbial imbalance, is associated with various diseases (1). Systemic antibiotics, bleach baths, or other antimicrobial interventions have been used in patients with Atopic Dermatitis (AD) to attempt to correct dysbiosis (4).

Unfortunately, in addition to promoting the development of antibiotic resistance in pathogens, the nonspecific use of antimicrobials also further disrupts the microbial ecosystem by killing both beneficial bacteria and pathogens. Therefore, the non-specific use of antimicrobials should be avoided when possible.

In this proposal, we describe a novel approach to attempt to treat dysbiosis of the skin surface. We have discovered that many of the strains of coagulase negative *Staphylococcus* (CoNS) that colonize healthy skin, such as *Staphylococcus epidermidis* (*S. epidermidis*), *Staphylococcus hominis*, *Staphylococcus warneri* and *Staphylococcus capitis*, produce antimicrobial activity against *Staphylococcus aureus* (SA). This activity is selective and kills many pathogens but does not inhibit the growth of the normal resident species. AD subjects have a deficiency in the abundance of bacteria that produce this activity. We hypothesize that reapplying the host's own antimicrobial bacteria will facilitate elimination of SA colonization.

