Some strains of *S. epidermidis*, often the dominant bacteria found in the skin microflora, produce various types of antimicrobials (10). Because of their potential to kill pathogens in vitro, these antimicrobials can provide antimicrobial protection against pathogens on the skin surface. We have published several examples of this (5, 11), and are characterizing more by using our innovative screening technique. These findings indicate that multiple CoNS species inhabiting the surface of normal human skin can be a source of antimicrobial activity and contribute directly to the skin's antimicrobial defenses. Also, this shows an additional benefit that may be derived from this study. By isolating diverse clones of antimicrobial bacteria we may discover several new antimicrobials

Figure 1 shows the high-throughput technique for screening CoNS strains that produce antimicrobial activity against SA. This technique enables us to determine the frequency of antimicrobial CoNS strains on the skin and then select them for transplant. Preliminary data shown in our introduction to the revised protocol has illustrated how AD patients colonized by SA have a lower frequency of antimicrobial CoNS species than normal healthy skin or *S. aureus*-negative AD patients. The profile of these antimicrobial CoNS was determined to be different from that of non-antimicrobial species by sequencing of the full-length 16S rRNA gene of each clone. These findings show that the human skin harbors diverse Staphylococcal strains providing antimicrobial activity, and that a low frequency of antimicrobial CoNS may partially account for the susceptibility of AD skin to infection by SA. All subjects studied to date harbor CoNS species that will inhibit SA. Thus, a source of microbes for AMT is available on most subjects even though AD subjects have fewer available with this activity than normal subjects.

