9.1 Skin swabs Samples

9.1.1. Skin Swab collection

The antecubital fossae bilaterally will be defined as the lesional swab location. The non-lesional swab location will be defined as the upper inner arm without AD skin. The designated site for swabbing will be marked with a pen and non-identifying digital photographs will be taken of the swabbing site for future visits. The designated site for swabbing will be measured for each subject, and the total area (cm x cm) recorded. Using a skin swab, the lateral edge of the swab will be rubbed across the measured area in a cross-wise manner while rotating the swab handle between the thumb and forefinger. Swabbing will be performed for at least 30 seconds. Up to 6 swabs may be obtained from each site.

9.1.2. *Staphylococcus aureus* Screening assay

Skin swabs will be collected from pre-measured areas of lesional and non-lesional skin per Section 9.1.1. Swabs will be resuspended in 1.5 mL tryptic soy broth (TSB) containing 15% (v/v) glycerol. Dilutions of culture medium will then be used to inoculate on mannitol salt agar plates with egg yolk for selective growth of *Staphylococcus* species and differentiation of coagulase-positive and coagulase-negative strains. Plates will be incubated for 24 hours in a 5% CO₂ incubator at 37° C. The plates will be evaluated for the presence of *S. aureus* colonies, which appear yellow with a surrounding clear zone.

9.1.3. 9.1.2. CFU Quantification of Live *Staphylococcus aureus*

Skin swabs will be collected from pre-measured areas of lesional and non-lesional skin per Section 9.1.1. Swabs will be suspended in 1.5 mL tryptic soy broth (TSB) containing 15% (v/v) glycerol and stored frozen at -80°C. Live CFUs of coagulase positive *S. aureus* will be determined by inoculation on a bacterial culture plate containing mannitol salt agar with egg yolk for selective growth of *Staphylococcus* spp. *S. aureus* will be conventionally distinguished from coagulase negative *Staphylococcus* according to mannitol metabolism and the egg yolk reaction, and coagulase positive and negative *Staphylococcus* will be quantified by manual counting of limiting dilutions of the stock solution.

9.1.4. Quantification of *Staphylococcus aureus*, *S. hominis*, *S. epidermidis*, and total *Staphylococcus* DNA by q PCR

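### The endpoint on transplanted (AMT) strains is tested as total live CoNS, which mixes transplanted with resident strains, and its companion quantity endpoint is tested as a percentage with no stated denominator

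*Combined protocol and SAP*

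**What the plan says.** Lesional item 1 in section 13.4.4 is titled "The abundance of the AMT bacterial strains on lesional skin at baseline and after 1 week BID application of AMT". The analysis beneath it is of live CoNS: "species on lesional skin will be compared from baseline (day 28) to Day 35", AMT against placebo, by a two-sided two-sample t-test. It is not restricted to transplanted or antimicrobial strains. Non-lesional item 2 follows the same pattern: live CoNS "species on non-lesional skin will be compared from baseline (day 28) to Day 35". (Section 13.4.4 numbers baseline and end of treatment as Day 28 and Day 35. They are taken here as Day 0 and Day 7 of the visit schedule.)

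Lesional item 2 and non-lesional item 3 are titled as the quantity of transplanted bacteria after stopping. Under item 2a, live antimicrobial Staph "species will be measured on lesional skin at baseline (day 28), Day 35 (after 7 days of cream application"), and then on the follow-up days. CFU counts are taken at each visit, but the variable compared between arms comes from a plan to "evaluate the percentage of antimicrobial species present at each time point". The plan does not say what it is a percentage of.

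On the laboratory side, the CFU section under 9.1 separates coagulase-positive from coagulase-negative colonies, which "will be quantified by manual counting of limiting dilutions of the stock solution". The activity screen that tells antimicrobial from other CoNS is described in section 1.3: "This technique enables us to determine the frequency of antimicrobial CoNS strains on the skin and then select them for transplant".

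**The concern.** The transplant consists of selected antimicrobial strains. A CoNS plate count cannot tell them from the CoNS already on the arm. At baseline and in the placebo arm the count contains no transplant at all. In the AMT arm it is the sum of residents and survivors, so a real gain in transplanted bacteria is diluted by whatever resident CoNS are present.

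The companion endpoint does not clearly close the gap, because a percentage is not an amount. Read literally, none of the four items tests how much antimicrobial CoNS is on the skin. At stake is the trial's ability to link a change in *S. aureus*, or the absence of one, to how much transplant was there. The primary endpoint is not affected.

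**Working it through.** **The plan's own figure.** The plan computes no figure for the CoNS endpoints. Its one sample-size figure (section 13.7) concerns *S. aureus*. With d = (192.86 − 19.186)/√((191.86² + 21.42²)/2) = 1.272 and 16 + 8 subjects, power is 0.802, so n = 24 reproduces. It has no bearing on this point.

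**Inputs.**
- From the documents: a target density of 10^5 CFU/cm² at application (section 3.1), arms of 18 and 9 (section 13.7), and the statement that "AD subjects have a deficiency in the abundance of bacteria that produce this activity" (section 1.1), with no percentage attached.
- Not in the documents, so assumed: resident CoNS density R, antimicrobial share of residents f, and surviving transplant T.

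**Rise over baseline, residents unchanged.**
- Total CoNS: log10((R + T)/R)
- Antimicrobial CoNS: log10((fR + T)/(fR))

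With f = 10%:

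| R (CFU/cm²) | T (CFU/cm²) | Total CoNS | Antimicrobial CoNS |
|---|---|---|---|
| 10^5 | 10^5 | log10(2) = 0.30 | log10(11) = 1.04 |
| 10^5 | 10^4 | log10(1.1) = 0.04 | log10(2) = 0.30 |
| 10^3 | 10^5 | log10(101) = 2.00 | log10(1001) = 3.00 |
| 10^3 | 10^4 | log10(11) = 1.04 | log10(101) = 2.00 |

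For any f below 1 the antimicrobial rise is the larger. Whether that changes the result depends on T relative to R.

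**Transplanted share of the end-of-treatment count, T/(T + R), with 10^5 applied.** For R = 10^3: 99% at full survival and 91% at 10% survival. For R = 10^5: 50% at full survival, 9% at 10% and 1% at 1%.

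**Power by simulation.** 18 against 9, t-test on log10 change, 4,000 runs. Assumed log10 SDs are 0.7 between subjects and 0.5 within. The antimicrobial share varies between and within subjects but is taken as measured without colony-sampling error, which flatters the antimicrobial measure somewhat.

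| T/R | Total CoNS | Antimicrobial, f = 5% / 20% / 50% |
|---|---|---|
| 0.1 | about 0.12 | 0.79 / 0.40 / 0.22 |
| 1 | 0.60 | 1.00 / 0.97 / 0.83 |
| 10 | at least 0.99 | at least 0.99 |

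**The percentage.** Read as percent of CoNS: hold antimicrobial CoNS at 10^4 and let other CoNS fall from 9×10^4 to 4.5×10^4. The percentage goes from 10^4/10^5 = 10% to 10^4/(5.5×10^4) = 18%, with no antimicrobial bacteria added. Read as percent of baseline, this cannot happen, and the log10 of the ratio is simply the change in log10 antimicrobial CoNS. The plan takes the percentage at baseline too, where a percent of baseline would be 100 for everyone. Percent of CoNS is therefore the likelier reading, though it is not stated.

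**The case against.** The strongest reply has four parts.

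1. **A reader might infer that the count is mostly resident flora and would hide the transplant.** The documents do not support that for treated skin at end of treatment. They give no resident CoNS density on lesional skin and no survival at the time of that swab, which is taken about 4 hours after the last of seven days of twice-daily applications. The pilot found CoNS near baseline and most of the transplant dead, but that was 24 hours after a single application. It shows that total CoNS can return to baseline after a dose of 10^5 CFU/cm², not what Day 7 will look like. The transplanted share could be anywhere from about 1% to 99%, and where the transplant is ten times the residents both measures serve equally well. This objection stands.

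2. **The percentage may mean percent of baseline.** The pilot figure reports relative CoNS that way, and item 2a offers the percentage as an allowance for baseline differences. This stands as far as it goes: the fault that can be shown is the missing denominator.

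3. **The information is not lost.** Item 2a already compares arms on antimicrobial species at end of treatment. This is true, but the comparison is of a percentage, and item 1 still tests something other than what it names.

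4. **Antimicrobial CoNS are not the AMT strains either, and can be zero.** Section 1.3 says all subjects studied so far carry some antimicrobial CoNS. If 5% of CoNS were antimicrobial and 24 colonies were screened (both assumed), 0.95^24 = 29% of samples would show none. Both halves stand and shape the fix.

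**Conclusion.** The point holds as a mismatch between the named and the analysed variable, at both skin sites. Item 1 (lesional) and item 2 (non-lesional) test a mixture of transplanted and resident CoNS. Item 2 (lesional) and item 3 (non-lesional) promise a quantity and test a percentage with an unstated base.

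The size cannot be fixed from the documents. With 10% of residents antimicrobial and 10^5 CFU/cm² added, the rise is 0.30 against 1.04 log10 at a resident density of 10^5, and 2.00 against 3.00 at 10^3. The loss of power is serious when survivors are few relative to residents, and nil when they far outnumber them. In none of the simulated cases did total CoNS do better. That supports changing the analysis. It does not support saying that the planned analysis will miss a successful transplant. These are secondary endpoints, so the matter is one of interpretation, not of the trial's main result.

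**What to change.** For lesional items 1 and 2 and non-lesional items 2 and 3:

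- Define the variable as log10 antimicrobial CoNS CFU/cm², that is, CoNS CFU/cm² times the antimicrobial fraction, with the denominator of that fraction stated as CoNS. Use the counts already planned under lesional item 2a and its non-lesional counterpart. The planned two-sample t-test can be kept.
- State in advance the value given to samples in which no antimicrobial CoNS is detected.
- Report total CoNS and the antimicrobial percentage as supportive.
- Describe antimicrobial CoNS as a closer surrogate for the AMT strains, not as identification of them.

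The cost is SAP wording, since the counts are already promised at these visits. Section 9.1 does not describe the activity screen on follow-up swabs or the number of colonies screened. A sentence there is needed so that the fraction and its detection limit are defined.

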3.1. Description of Study Design

This is a single site, double blind placebo controlled study, which will assess the efficacy, safety, and steady state of Autologous Microbiome Transplant (AMT) cream in adults with AD. After providing informed consent, patients will be assessed for study eligibility at the screening visit, in which participants will consent to all of the study experiments separately. Subjects that withdraw from the study will be replaced. Eligible subjects will be randomized to receive either AMT cream or placebo in a 2:1 allocation ratio (AMT cream: placebo).

Subjects will be instructed to apply either the AMT or vehicle cream to both arms twice a day for seven days. Both subjects and clinical investigators will be blinded. Optional follow-up visits to assess clinical effect and steady state may occur at 1 and 4 hours after initial cream application if the subjects are willing to return at these time points. 4 days after the treatment visit, subjects will return to the clinic for fresh aliquots of the AMT and vehicle creams as well as to assess safety and clinical effect. Subjects will return to clinic after the seven day course of AMT or vehicle creams for clinical and safety assessments. Subjects will then be asked to return to the clinic 1 day after completion of the AMT or vehicle cream course for additional safety and clinical effect assessments. Subsequently, subjects will return for additional follow-up visits only if their lesional atopic dermatitis sites have not yet returned to baseline (*S. aureus* is no longer inhibited and *Staph species* from the AMT cream is zero). Up to 27 subjects will be recruited for this entire study. The duration of this study is approximately 2 months. We anticipate the entire study duration will be approximately 2 years total, and that it will take approximately 1 year to reach recruitment and enrollment goals for this study. The study flow diagram is provided in Figure 1.

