
Optional Visit 1 (1 hour after cream application +/- 2 hours): Subjects will have the option to return to clinic for an optional visit approximately 1 hour after AMT cream application. At this optional visit, up to 12 skin swabs will be taken of the lesional and non-lesional skin on the arms (one culture swab and one to two DNA swabs for lesional and non-lesional skin of each arm). This visit will take approximately 15 minutes.

Optional Visit 2 (4 hours after cream application +/- 2 hours): Subjects will have the option to return to clinic for an optional visit approximately 4 hours after AMT cream application. At this optional visit, up to 12 skin swabs will be taken of the lesional arms and non-lesional skin on the arms (one culture swab and one to two DNA swabs for lesional and non-lesional skin of each arm). This visit will take approximately 15 minutes.

Visit 4 (Day 4 +/- 5): Subjects will return to the clinic to pick up fresh aliquots of the AMT or vehicle creams, and to return approximately 4 hours after last cream application. Any adverse events will be recorded. Subjects will be asked to refrain from bathing, exercising, or showering starting at 12:01am of Visit 4. Vital signs will be taken. Subject diaries will be collected at this time and a new subject diary will be dispensed to assess for cream application appliance. Used aliquots of cream will be collected at this visit. The localized SCORAD, modified EASI, global EASI and SCORAD grading scale will be used to rate the severity of the lesional AD skin on the subject's bilateral arms, and the extent of lesional AD skin on each arm will be recorded. Digital photographs of the lesional skin on both arms will be taken. Each photograph will also include a ruler so the scale of the lesions can be determined, as well as a card with the subject's identification number, visit date, and photograph location so that the photographs can be identified when uploaded. Next, one culture swab and one to two DNA swabs will be taken from the eczematous skin from each arm, and one culture swab and one to two DNA swabs will be taken from the non-lesional skin on each upper inner arm for a total of up to twelve (12) swabs. We expect this visit to take approximately 15 minutes.

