13.2.2 Secondary Endpoint(s)/Outcome(s)

Secondary Lesional AD skin:

1. The abundance of the AMT bacterial strains on lesional skin at baseline and after 1 week BID application of AMT.
2. The quantity of transplanted bacteria on lesional skin after stopping AMT cream 1 day, 2 days, and 4 days after last application.
3. The change in abundance of *Staph aureus* on lesional skin from baseline to 1 day, 2 days, and 4 days after stopping AMT.
4. Change in clinical assessments, including SCORAD, modified EASI, and EASI after 1 week BID application of AMT.
5. Identify lesional skin microbiome by DNA sequencing from baseline and after 1 week BID application of AMT.
6. Evaluate the lesional skin microbiome transcriptome by RNA-sequencing analysis from baseline and after 1 week BID application of AMT.

Secondary Non-lesional skin:

1. The abundance of *Staph aureus* at baseline and after 1 week BID application of AMT on non-lesional skin.
2. The abundance of AMT bacterial strains on non-lesional skin at baseline and after 1 week BID application of AMT.
3. The quantity of transplanted bacteria on non-lesional skin after stopping AMT cream 1 day, 2 days, and 4 days after last application.
4. The change in abundance of *Staph aureus* on non-lesional skin from baseline to 1 day, 2 days, and 4 days after stopping AMT.
5. Identify non-lesional skin microbiome by DNA sequencing from baseline and after 1 week BID application of AMT.
6. Evaluate the non-lesional skin microbiome transcriptome by RNA-sequencing analysis from baseline and after 1 week BID application of AMT.

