13.7 Sample Size Considerations

Number of *S. aureus* colonies will be a continuous variable, and change in *S. aureus* abundance will be measured as the absolute difference in number of colony-forming units at specified time points.

The sample size was calculated using G-Power Data Analysis software for a two-tailed t-test for independent samples, type II error rate of 0.2, and type I error rate of 0.05. The values used in the analysis were determined from our pilot study in which we quantified the reduction in *S. aureus* on the forearms of 5 atopic dermatitis patients twenty-four hours after treatment with a live microbiome transplant. Since the sample size was small in this study, we used the median and median average deviation as measures of central tendency. The median *S. aureus* present on the forearms of atopic dermatitis patients at baseline was 192.86 CFU/cm² with deviation of 191.86. We observed that a log-base 10 reduction by 1 of the number of bacteria present on the forearms to be a clinically significant reduction at 24 hours, with deviation of 21.42. Using $\mu_1 = 192.86$, $\mu_2 = 19.186$, and $\sigma_1 = 191.86$, and $\sigma_2 = 21.42$, the total sample size necessary to see this difference would be $n=24$ for an unequal allocation of subjects 2:1 in the treatment to placebo groups.

Assuming a drop-out rate of 20%, we propose a total $n=27$, with $n= 18$ in the treatment group and $n= 9$ in the placebo group. Assignment to treatment or placebo groups will be determined using simple randomization with an online random number generator.

This sample size is reasonable and practical within the scope of this funding mechanism and recruitment capabilities.

An intention-to-treat analysis will be conducted that includes all subjects who had at least one follow-up visit after intervention. A per-protocol analysis will also be conducted that includes all subjects who were compliant with the full intervention regimen with no major protocol violations.

14. Identification and Access to Source Data

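### The analyses for S. aureus change 1, 2 and 4 days after stopping (13.4.4, lesional 3a and non-lesional 4a) list only baseline and on-treatment times, so they do not match their endpoints

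*Combined protocol and SAP*

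**What the plan says.** Section 13.2.2, lesional item 3, defines the endpoint as the change in S. aureus abundance "on lesional skin from baseline to 1 day, 2 days, and 4 days after stopping AMT". Non-lesional item 4 is the parallel endpoint, and its heading in 13.4.4 reads "on non-lesional skin from baseline to 1 day, 2 days, and 4 days after stopping AMT".

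The analysis text below those headings names other times. Lesional 3a states that live S. aureus "on lesional skin will be evaluated using CFU counting at baseline, 1 hour, and 4 hours after initial application of AMT or placebo cream", followed by Day 4 and Day 7 of the course. Non-lesional 4a states that it "on non-lesional skin will be evaluated using CFU counting at baseline, 1 hour, and 4 hours after initial application of AMT or placebo cream", with the same two later times. Both compare the arms at each listed time with a two-sided independent-samples t-test at 0.05.

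The plan does name post-stopping days for a different measurement. Lesional 2a, on antimicrobial CoNS, lists baseline and "Day 35 (after 7 days of cream application), Day 36, Day 37, and Day 39", and non-lesional 3a does likewise.

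In section 8.3 and Table 1, swabs are scheduled at Visits 6, 7 and 8 (Days 8, 9 and 11), each with a window of +/- 7 days.

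**The concern.** Each endpoint asks what happens to S. aureus once the cream is stopped. The analysis written for it ends when the cream ends. Section 1.1 gives the duration of any S. aureus reduction as something the study is meant to find out, and section 2 makes the rate of reappearance an objective at both skin sites. If 3a and 4a are followed exactly, the S. aureus counts from Visits 6 to 8 are collected but the arms are never compared on them. An analyst who fills the gap after unblinding would be choosing the comparison with the data in view.

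**Working it through.** The plan gives no figure to reproduce here. The check sets the required times against the listed times, and then looks for another section that fills the gap.

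**Step 1: required against listed.**

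| Source | Times after baseline |
|---|---|
| Endpoints: 13.2.2, lesional 3 and non-lesional 4 | 1, 2 and 4 days after the last application |
| Analyses: 13.4.4, lesional 3a and non-lesional 4a | 1 h, 4 h, Day 4, Day 7 |
| In both | none |

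Day 7 is not a post-stopping time: 8.3 places Visit 5 about 4 hours after the last application. Comparisons required: 3 times x 2 sites = 6. Comparisons listed: 0.

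**Step 2: is the comparison written elsewhere?**

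- 13.4.2 (primary) and 13.4.4 non-lesional 1a stop at Day 35, which is end of treatment in that numbering.
- 13.4.4 lesional 2a and non-lesional 3a list the post-stopping days, but for antimicrobial CoNS only.
- 13.7 says that change in S. aureus "abundance will be measured as the absolute difference in number of colony-forming units at specified time points". This defines change but names no times.

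So no section supplies the 6 comparisons. The Day 7 tests in 3a and 4a also fall at the same time as those in 13.4.2 and non-lesional 1a. That suggests text placed under the wrong heading.

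**Step 3: day numbering.** Section 13.4 counts baseline as Day 28, while 8.3 counts it as Day 0. Subtracting 28:

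- 28 -> 0, 35 -> 7, 36 -> 8, 37 -> 9, 39 -> 11, which matches the visit schedule.
- 38 -> 10, which is no scheduled visit. Lesional 2a and non-lesional 3a each give both Day 39 and Day 38 as the last time.

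**Step 4: visit windows.** V6: 8 +/- 7 = Days 1-15. V7: 9 +/- 7 = Days 2-16. V8: 11 +/- 7 = Days 4-18. Days 4-15 lie in all three, so a visit label alone does not fix the time since stopping.

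**Step 5: multiplicity once the tests are written.** If the tests were independent (an assumption), the chance of at least one false positive at 0.05 is 1 - 0.95^3 = 14.3% per site and 1 - 0.95^6 = 26.5% over both sites. The samples come from the same subjects, so the tests will be correlated and these figures only illustrate the scale.

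**The case against.** The best reply is that the plan's meaning is clear. The headings in 13.4.4 state the contrast, 13.2.2 repeats it, and 13.7 says how change is measured. The assay, arms, test and alpha are given, and the swabs are scheduled. On this view it is a wrong list of times under a right heading, for secondary endpoints only.

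Most of that stands: the intent can be inferred and no data are lost. What does not stand is that the comparison is therefore pre-specified. The test in 3a and 4a applies to the times those items list. The CoNS items show that the authors named post-stopping days where they meant to use them.

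Two stronger readings do not hold.

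- A reader might infer that the 1 h and 4 h comparisons rest entirely on optional attendance, because 3.1 says that optional follow-up visits "may occur at 1 and 4 hours after initial cream application if the subjects are willing to return at these time points". But 8.3 also has swabs within the scheduled Treatment Visit, on lesional and non-lesional skin, from 5 minutes to an hour after application. Some or all of the 1 h data could come from these.
- A reader might count non-lesional items 5 and 6 of 13.4.4 as further endpoints with the wrong analysis, because their text names lesional skin. They sit under the non-lesional heading and 13.2.2 names the right site. This is a copying slip in descriptive items with no between-arm test.

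**Conclusion.** The point holds as a mismatch between endpoint and analysis for two secondary endpoints: 0 of 6 post-stopping S. aureus comparisons are listed. It rests on the text alone and on no assumption about effect size, variance or dropout. The primary endpoint and the CoNS analyses are not affected by it.

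A reader might go further and state how many days off target each post-stopping sample could be. The windows overlap, but the documents do not fix the day of the last application, or state that Visits 6 to 8 fall in order on separate days. No such range can be given.

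A reader might also infer that attendance after the 1-day visit is selected on outcome, and that one later visit is biased more than another. Section 3.1 does make later return conditional on the lesional site not having returned to baseline. However, 6.2, 8.3 and Table 1 schedule the visits without that condition, and no turnaround time for the counts is given. What can be said is that these sections disagree on who contributes 2-day and 4-day data.

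**What to change.** Before unblinding:

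1. Rewrite lesional 3a and non-lesional 4a to compare arms on S. aureus change from baseline (Day 0) at 1, 2 and 4 days after the last application (V6, V7, V8; Days 8, 9, 11), with the independent-samples t-test already named. The 1 h, 4 h and Day 4 comparisons may stay as additional on-treatment analyses.
2. Align the day numbering in 13.4 with the Day 0/7/8/9/11 schedule and settle Day 38 against Day 39.
3. Record the actual time since the last application for each sample, and set in advance one rule assigning samples to the 1-, 2- and 4-day times.
4. State that these are six secondary tests at 0.05 without multiplicity control, to be read as such.
5. Reconcile 3.1 with 6.2, 8.3 and Table 1 on who returns after the 1-day visit.
6. Correct non-lesional items 5 and 6 in 13.4.4 to name non-lesional skin.

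The cost is wording, one recorded field, some analysis work and a protocol clarification for item 5. The assignment rule may leave some samples outside the target times. No swabs or visits are needed beyond those in 8.3 and Table 1.
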